IRB Member:	 YES	 NO	Date: _____
Social/Behavioral Research Course:	 YES	 NO	Date: _____
IRB accepts Alternative Training:	 YES	 NO	Date: _____
	 YES	 NO	Date: _____

Training Reviewer: _____ Date: _____ 7/9/2024

PROTOCOL APPROVAL

(for office use only)

EXEMPT

Declared by: _____ Date: _____

EXPEDITED

Approved - Reviewer 1: _____ [name]. Date: _____ 10/28/2024

Approved - Reviewer 2: _____ Date: _____

FULL REVIEW

Referred for Full Review: _____ Date: _____

Approved: _____ Date: _____

Date of Full Review (attach minutes): _____

Subject: Opportunity to Participate in a Research Project

Dear PVAMU students,

My name is [name] and I am an Assistant Professor in the Psychology Department at PV. I am emailing you to invite you to be part of a research project about virtual group mental health therapy for Black college students. The purpose of the research is to determine how group telehealth therapy compares to individual telehealth therapy.

If you participate in this project, you will be asked to first complete two mental health assessments. You may then be asked to continue the study and take part in a 12-week virtual therapy program. During this 12-week period you will be asked to complete activities related to the therapy, take mental health assessments, and provide feedback on your experience.

If you participate in this study, you may be eligible to earn up to \$305.00 in the form of an Amazon gift card over approximately 12 weeks of your time. Participation is voluntary, but I hope you will choose to be part of this project. *To participate in the study you must be a Black PVAMU college student of 18 years or older.*

For more information, or to sign up, go to [enter study website here] or contact me at [contact].

Thanks,

[name]

PHQ-9

Over the last 2 weeks, how often have you been bothered by any of the following problems?

Scale: 0 = not at all; 1 = several days; 2 = more than half the days; 3 = nearly every day

1. Little interest or pleasure in doing things
2. Feeling down, depressed, or hopeless
3. Trouble falling or staying asleep, or sleeping too much
4. Feeling tired or having little energy
5. Poor appetite or overeating
6. Feeling bad about yourself or that you are a failure or have let yourself or your family down
7. Trouble concentrating on things, such as reading the newspaper or watching television
8. Moving or speaking so slowly that other people could have noticed. Or the opposite being so fidgety or restless that you have been moving around a lot more than usual
9. Thoughts that you would be better off dead, or of hurting yourself

GAD-7

Over the last two weeks, how often have you been bothered by the following problems?

Scale: 0 = not at all; 1 = several days; 2 = more than half the days; 3 = nearly every day

1. Feeling nervous, anxious, or on edge
2. Not being able to stop or control worrying
3. Worrying too much about different things
4. Trouble relaxing
5. Being so restless that it is hard to sit still
6. Becoming easily annoyed or irritable
7. Feeling afraid, as if something awful might happen

Engagement

On a scale from 1 to 5 with 1 being not at all to 5 being completely, rate how much the following statement applies to your experience with the telehealth therapy program:

1. I was interested in the therapy
2. I was intrigued when I used the telehealth therapy services
3. I was focused when I used the telehealth therapy services
4. I enjoyed using the telehealth therapy services

5. It was boring to use the telehealth therapy services
6. I felt frustrated using the telehealth therapy services
7. I found the telehealth services confusing
8. I felt unmotivated to use the telehealth services

User Feedback Experience

1. What, if anything, did you enjoy about your experience in using the guided telehealth therapy?
2. What, if anything, could be improved about your experience in using the guided telehealth therapy?
3. Did you feel the psychoeducational content was culturally relevant to you as a Black individual? Please explain

Statistical Analysis Plan

Official Study Title: Guided group telehealth to deliver evidence-based therapeutic care to Black college students

NCT Number:

Date of Document: 03/10/2025

Statistical Analysis Plan

To test the primary hypothesis that participants in the Guided Group Telehealth (GGT) condition will experience reductions in depression and anxiety comparable to those in the Individual Telehealth (IT) condition, we will use a mixed-design repeated measures ANOVA. The within-subjects factor will be time (baseline, week 4, week 8, and week 12), and the between-subjects factor will be therapy condition (GGT vs. IT). The dependent variables will be PHQ-9 and GAD-7 scores, measuring depression and anxiety, respectively. Interaction effects will be examined to assess whether changes in symptom severity over time differ between the two conditions. For secondary analyses, we will use independent samples t-tests to compare user engagement and user experience scores between the two conditions at week 12. Descriptive statistics will be used to summarize engagement data, including participation rates, message frequency, and task completion. Additionally, qualitative analysis will be conducted on open-ended responses from the user experience survey to identify common themes related to participants' satisfaction and perceived effectiveness of the intervention. All analyses will be conducted using an alpha level of 0.05, and effect sizes will be reported alongside p-values. If violations of normality or sphericity are detected, appropriate corrections, such as Greenhouse-Geisser adjustments or nonparametric alternatives, will be applied.

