Participants will access the study via an online link provided by email or via word of mouth. They will first answer a question to assess their suicide risk. If they have not had suicidal thoughts in the previous three weeks, they will continue on to the study. If they indicate they have had such thoughts in the prior three weeks, they will be disqualified from the study and a screen will appear with contact information regarding mental health resources. [name] will then reach out to Student Counseling Services and ask them to reach out to the students to follow-up and provide additional support. For those students who continue with the study, they will take the PHQ-9 and the GAD-7 to measure their depression and anxiety levels. If they score 5 or above on either test they will be invited to participate in the therapy part of the study. In this part of the study the participant will be assigned to either receive individual teletherapy or group teletherapy for 12 weeks. This therapy takes place via text. Participants may be asked to read psychoeducational materials and complete homework assignments. Participants assigned to the individual therapy, will receive support in the form of direct asynchronous communication with the therapist. Participants assigned to the group therapy will receive support in the form of direct asynchronous communication with the therapist and asynchronous communication with peers struggling with similar issues. Throughout the at week 4, 8 and 12 of therapy, participants will take the GAD-7, PHQ-9, and self-report questionnaires to measure their engagement and experience.

Describe the location where research activities will take place:

The research will take place on participants personal electronic devices by logging on to the web-based TheraGroup platform. TheraGroup is a proprietary real-time virtual based platform that provides text based group therapy. It is a cloud software that offers HIPAA compliant asynchronous text chat.

How long will the participants be engaged in research? (length of time, i.e. 15 minutes on day 1, etc.):

up to 12 weeks

During data collection, describe what steps will be taken to ensure participant privacy:

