The current mental health crisis across college campuses particularly impacts students at Historically Black Colleges and Universities (HBCUs), who, compared to their Predominantly White Institution (PWI) counterparts, have fewer resources and less funding to support student psychological health [1]. While online therapy offers benefits, it does not solve the issue that the number of available therapists is insufficient to treat the number of students seeking help [2]. A promising solution is to increase opportunities for group therapy, which is equivalent to individual therapy in terms of outcomes [3]. As such, the purpose of our study is to assess the impact of an online, group text based therapy (one mental health counselor to many students) against a one-to-one (one mental health counselor to one student) therapy among HBCU students. Specifically, we will compare a HIPPA compliant, guided group telehealth (GGT) therapy (group therapy) called TheraGroup against a HIPPA compliant individual telehealth (IT) therapy (individual therapy) on measures of engagement, user experience, and mental health outcomes. If outcome measures in the GGT group are in line with outcome measures in the IT group, the feasibility study will serve as a precursor to testing the effects

RISKS AND BENEFITS

Describe any potential risks or discomforts to the participant (including physical, psychological and/or social):

Risks to subjects are rated as "Low", "Medium", "High". Do not say "none".

participants may be at risk of psychological harm. As the survey measures and therapy intervention ask participants to explore their mental health, specifically difficulties they may be having and traumatic events they have previously experienced, this process may exacerbate pre-existing mental health

Describe any potential benefits to the research participant or society:

Participants in this study will benefit from receiving mental health treatment from qualified professionals. Identifying effective group telehealth therapies to increase the access to mental health interventions contributes not only to the expansion of scientific knowledge within the field of mental health, but also to practical applications. Based on the findings of this study, interventions, trainings, and supports can be developed to treat mental illness in Black college students. This has potential

Describe alternatives to participation/opportunity to withdraw:

Participants may withdraw at any time

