SUBJECT RECRUITMENT

Number of participants (target population): 8000 Ages of Participants: 18 years or older

Gender of subjects: Male

Maximum anticipated sample size: 200

Female

What are the selection criteria for participation (i.e. include target population and maximum anticipated sample size)?
For clarification on target population and maximum anticipated sample size, please refer to FAQ #35 on the [PVAMU IRB website](#).

Participants must be Black college students attending Prairie View A&M University (PVAMU) who are at least 18 years of age, and who qualify for psychological clinical intervention based on their current levels of depression and anxiety.

Do the criteria for selection exclude individuals based on gender, culture, language, economic status or ethnicity?

Yes No

If yes, please justify exclusion:

We are excluding non-Black individuals. The telehealth program we are testing is tailored for the Black population and thus we would like to test it on a matching sample.

Are there any special physical or psychological conditions of subjects? (If so, please describe.)

Participants who score a 5 or more on the GAD-7 (anxiety) or the PHQ-9 (depression) will qualify for the therapeutic intervention aspect of the study. These scores represent at least a minimal level of anxiety and depression.

Source of participants:

PVAMU students (provide explanation below) Community (provide explanation below)
 Schools* (provide explanation below) Other (provide explanation below)

Participants will be Black college students attending PVAMU

For studies involving schools:

Does the study involve a school district? Yes No

If Yes, which school district(s): _____

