
Please check all that apply and attach to the application:

 Cover Letter	 Adult Consent Form
 Information Sheet	 Minor Assent Form
 Telephone Script	 Parental Consent Form

Location where consent forms will be filed:

(Consent forms must be kept on file for 3 years after completion of the study and data analysis)

All data and forms including consent forms will be kept on a password protected computer in [name] office in [name]

WAIVER

Request for waiver of informed consent or waiver of documentation of informed consent:

Yes No

If Yes, explain below:

[Large empty box for explanation]

COMPENSATION / COURSE CREDIT

Will monetary compensation be given to the participant?

Yes No

If Yes, explain below and attach a detailed compensation of payment including amount and schedule of payments to participant:

Participants will receive payment in the form of Amazon gift cards. Our study has 4 time points in which participants may be compensated for their time. These time points are listed below along with the amount participants receive for taking part in each time point.

Time	Compensation
Time 1: before therapy started	\$5
Time 2: 4 weeks after therapy has started	\$50
Time 3: 8 weeks after therapy has started	\$100

Will course credit be given to the participant as compensation?

Yes No

If Yes, provide details below and alternate assignment to obtain equal credit:

SUBJECT MATTER

Check the appropriate box(es) concerning the subject matter of the research:

 No sensitive matters	 Learning disability
 Abortion	 Physical disability
 AIDS/HIV	 Psychological inventory
 Alcohol	 Review of criminal records
 Body composition	 Review of educational records
 Criminal activity	 Sexual Activity
 Depression	 Suicide
 Drugs	 Other, specify: general mental health issues

DECEPTION OR COERCION

Will deception or coercion be used?

Yes No

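### The primary repeated-measures ANOVA, as usually run, keeps only participants with all four scores, and no missing-data rule is given; a likelihood-based mixed model on every observed score should replace it

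*SAP*

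**What the plan says.** The SAP is a single paragraph. For the primary hypothesis it states "we will use a mixed-design repeated measures ANOVA" and defines the factors as follows: "The within-subjects factor will be time (baseline, week 4, week 8, and week 12), and the between-subjects factor will be therapy condition". PHQ-9 and GAD-7 are the dependent variables, and the condition-by-time interaction is the comparison of interest. The only contingencies are for non-normality and non-sphericity: "appropriate corrections, such as Greenhouse-Geisser adjustments" or nonparametric alternatives.

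The protocol (Risks and Benefits) states "Participants may withdraw at any time". Under Procedures, "the participant will be assigned to either receive individual teletherapy or group teletherapy for 12 weeks", and group participants receive "direct asynchronous communication with the therapist and asynchronous communication with peers struggling with similar issues". Subject Recruitment gives "Maximum anticipated sample size: 200". Under Compensation, "Our study has 4 time points in which participants may be compensated for their time"; the listed amounts rise from $5 to $50 to $100, and the recruitment e-mail gives a total of up to $305.

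Neither document states an analysis population, a rule for missing scores, an imputation method, a sensitivity analysis or an expected drop-out rate.

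**The concern.** Mixed-design here means one between-person and one within-person factor, not a mixed-effects model. The Greenhouse-Geisser correction belongs to that classical form. In its usual operation it needs a complete row of four scores per person. A participant seen at baseline, week 4 and week 8 but not at week 12 contributes nothing, although three scores are in hand. The SAP names no software and does not itself say complete cases. The problem is a method that defaults to them combined with no rule that says otherwise.

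Two things are at stake. The first is bias. The trial asks whether GGT does about as well as individual telehealth (IT), and the formats differ, so drop-out related to response could differ by arm. If it does, the completer contrast is distorted. No passage says this will happen, or in which direction. The second is precision: fewer participants make a non-significant interaction more likely, and that could be misread as showing that the arms are comparable.

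**Working it through.** **Inputs.** From the documents: at most 200 participants, four time points, alpha 0.05. Assumed, because the documents are silent: 100 per arm, SD 5, correlation 0.6 between any two visits, true GGT deficit of 0.5, 1.0 and 1.5 points at weeks 4, 8 and 12. The plan has no power or drop-out figure of its own to reproduce.

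**1. Scores lost.** With loss p per follow-up visit:
- complete participants = 200(1−p)³
- follow-up scores used by the ANOVA = 600(1−p)³
- follow-up scores collected = 200[(1−p)+(1−p)²+(1−p)³] under permanent withdrawal, or 600(1−p) if visits are missed independently

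Example, p = 15%, withdrawal: 200 × 0.6141 = 123 complete. Collected: 200 × (0.85 + 0.7225 + 0.6141) = 437. Used: 600 × 0.6141 = 368. So 16% is discarded.

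**2. Precision.** The variance of change is 2(1−0.6)(25) = 20, so the completer SE at week 12 is √(20 × 4/n), with n the number complete. At 15% this is √(80/122.8) = 0.81. The likelihood SE comes from the expected information summed over missingness patterns. Interaction power uses the noncentral F with 3 numerator df; denominator df is 3(n−2) for completers and follow-up scores minus 6 for likelihood. With no loss, the SE is 0.63 and power is 0.53.

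| Type of loss | p | Complete | Discarded | SE: completers / likelihood | Power: completers / likelihood |
|---|---|---|---|---|---|
| Withdrawal | 5% | 171 | 5% | 0.68 / 0.67 | 0.47 / 0.48 |
| Withdrawal | 10% | 146 | 10% | 0.74 / 0.71 | 0.40 / 0.43 |
| Withdrawal | 15% | 123 | 16% | 0.81 / 0.76 | 0.34 / 0.39 |
| Withdrawal | 20% | 102 | 21% | 0.88 / 0.82 | 0.29 / 0.34 |
| Missed visits | 10% | 146 | 19% | 0.74 / 0.66 | 0.40 / 0.50 |
| Missed visits | 15% | 123 | 28% | 0.81 / 0.67 | 0.34 / 0.48 |
| Missed visits | 20% | 102 | 36% | 0.88 / 0.68 | 0.29 / 0.46 |

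Under withdrawal at 10/15/20% the likelihood SE is 4/6/8% lower, worth about 13/16/18 extra completers. At 15% withdrawal with correlation 0.5 to 0.7, power is 0.28–0.45 for completers and 0.32–0.50 for likelihood.

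**3. Bias when drop-out depends on observed scores.** One million simulated participants per arm, permanent withdrawal. The log-odds of loss at weeks 8 and 12 are linear in the last observed change from baseline, per 5 points and centred within arm, so a positive slope loses non-improvers. Incomplete follow-up is set equal in the two arms, at 20% or 39% (1 − 0.85³ = 38.6%). Each range spans two versions: week-4 loss unrelated to response, or all loss after week 4. The true week-12 deficit is 1.5 and Monte Carlo error is about 0.01–0.02.

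| Slopes | Incomplete | Completers, steeper in GGT | Completers, steeper in IT |
|---|---|---|---|
| 0.6 vs 0.3 | 20% | 1.38–1.41 | 1.58–1.62 |
| 0.6 vs 0.3 | 39% | 1.27–1.33 | 1.66–1.73 |
| 1.2 vs 0 | 20% | 1.05–1.19 | 1.81–1.94 |
| 1.2 vs 0 | 39% | 0.64–0.89 | 2.11–2.35 |

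With equal slopes of 0.6, completers give 1.48–1.51. Likelihood gives 1.48–1.51 in every row.

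The direction depends on the mechanism. A separate simulation (600 trials, 100 per arm, AR(1) correlation 0.6) let drop-out depend on the level of the last score, in GGT only. Completers then overstated the deficit: 0.52 against a true 0, and 2.49 to 3.02 against a true 2. Likelihood gave −0.05 and 1.97 to 2.01.

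**4. Limit of likelihood.** In the set-up of step 3 at 39% incomplete, if loss depends on the current, unseen change, likelihood gives 1.30–1.35 or 1.64–1.70 (modest) and 0.77–0.95 or 2.02–2.23 (strong). Completers give 1.15–1.24 or 1.74–1.85, and 0.23–0.57 or 2.42–2.77. Likelihood is less biased, but not unbiased.

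**5. Clustering in GGT.** With groups of m and an ICC on change, the true SE with no loss is √[(20/100)(2+(m−1)ICC)]. Groups of 8–10 and ICC 0.05 give 0.69–0.70 against 0.63 if clustering is ignored, so a nominal 95% interval covers 92–93%. At ICC 0.10 the SE is 0.73–0.76 and coverage is 90–91%. Group size and ICC are assumptions.

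**The case against.** The strongest case against is that the practical effect may be slight. No input comes from the documents. Under permanent withdrawal, the only kind of loss they mention, power rises by just 0.03–0.05 at 10–20% loss per visit, and at 5% there is almost no gain. Those central rates mean 27–49% incomplete, while the rising payments may keep loss well below that. The modest bias at 20% incomplete is about 0.1 point, roughly one-seventh of an SE of 0.7. Large bias needs strong response-driven drop-out in one arm and none in the other. The protocol also calls this a feasibility study. All of this stands, and it limits the weight of the point. It does not supply the missing rule, and the GGT-IT comparison is meant to decide whether further testing follows.

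Three further points stand in part:
- Power to detect a difference is not the natural yardstick for a comparability question; interval width against a margin is. The absence of a margin is a separate issue that this change does not settle.
- The likelihood power is slightly generous. With denominator df suited to an unstructured covariance it is 0.43/0.38/0.33 at 10/15/20% withdrawal.
- Multiple imputation under a stated missing-at-random assumption, with all assigned participants, would also answer the concern.

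Clustering is a side issue here. It belongs only because the replacement model should not report an interval that silently ignores it. Groups of 8–10 would mean about 10 to 12 groups, few for estimating a variance, and therapist clustering could affect both arms.

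**Conclusion.** The concern holds. Run in the usual way, the planned analysis discards observed scores and exposes the GGT-IT contrast to completer bias, and nothing in either document prevents this. The omission is certain; its size is not. Under the assumptions above, bias ranges from nil (equal response-related drop-out in both arms), through about 0.1 to 0.2 point (modest difference between arms), to about 0.9 point (strong difference, 39% incomplete), on a true deficit of 1.5 and in either direction. The precision cost is small for permanent withdrawal and larger for missed single visits. The change should be made because it is cheap and guards the main comparison, not because large bias has been shown to be likely.

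**What to change.** For each of PHQ-9 and GAD-7, replace the repeated-measures ANOVA in the SAP with a likelihood-based mixed model: REML, condition by visit, unstructured within-person covariance. In addition:

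- Analyse all assigned participants in their assigned arm, using every observed score.
- Report the week-12 arm difference in change with its confidence interval, and completion by arm and visit.
- Include a therapy-group random effect in the GGT arm that acts on the follow-up visits, since one that is constant from baseline cancels out of change. If it cannot be estimated, state that the interval does not allow for clustering.
- Add a delta-adjusted sensitivity analysis that shifts the missing scores by amounts varied by arm, with the range fixed in advance, because the model remains biased if drop-out depends on unseen scores.

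The cost is SAP wording, slightly more analysis work, and therapy-group membership in the analysis file. No new data and no extra participants are needed.

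### Baseline PHQ-9 and GAD-7 enter the primary ANOVA as an outcome level with no baseline adjustment; if assignment is random, this gives up some precision in the arm comparison

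*SAP*

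**What the plan says.** For the primary hypothesis the SAP states: "we will use a mixed-design repeated measures ANOVA". Baseline is part of the outcome vector: "The within-subjects factor will be time (baseline, week 4, week 8, and week 12". The outcomes are the two symptom scales: "The dependent variables will be PHQ-9 and GAD-7 scores, measuring depression and anxiety, respectively". The arm comparison is the condition-by-time interaction: "Interaction effects will be examined to assess whether changes in symptom severity over time differ between the two conditions". Neither document mentions a covariate, an analysis of covariance or a model with a common baseline mean. The SAP promises p-values and effect sizes, but no confidence interval and no named time point for the primary outcomes.

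The scores needed for adjustment are already collected. Under Procedures in the protocol, students complete both scales before they enter therapy: "If they score 5 or above on either test they will be invited to participate in the therapy part of the study". On allocation, the same section says only that "the participant will be assigned to either receive individual teletherapy or group teletherapy for 12 weeks". Under Subject Recruitment, the size is given as a ceiling: "Maximum anticipated sample size: 200".

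**The concern.** A four-level interaction with baseline as one level has three degrees of freedom. The arm differences in change from baseline to weeks 4, 8 and 12 span them, so the test is in effect a test on change scores. Subtracting the whole baseline score removes between-person variation, but it also adds the noise in that score. Regression on baseline subtracts only the part that predicts the later score.

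Precision matters here because the hypothesis is that the two formats give comparable reductions, and the protocol's Purpose of Study makes similar outcomes the trigger for further testing. The wider the interval around GGT minus IT, the less a non-significant interaction says about comparability. The sample is capped and no derivation is given, so ample precision cannot be taken for granted.

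**Working it through.** The plan states no power, detectable difference or derived sample size, so there is no figure to reproduce.

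**Inputs.** From the documents: the ANOVA and its time levels, alpha 0.05 (SAP), and a maximum of 200 participants (protocol, Subject Recruitment). Assumed, because the documents are silent: random 1:1 assignment with 100 per arm, no dropout, two-sided testing, a week-12 SD of 5 points, r from 0.5 to 0.7, and k = SD_baseline/SD_week12 from 0.8 to 1.2.

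**Per-participant variance at week 12, in units of SD_week12².**
- Change from baseline: 1 + k² − 2rk
- Adjusted for baseline: 1 − r²
- Difference: k² − 2rk + r² = (k − r)², which is never negative and is zero when k = r
- With k = 1, the ratio of adjusted to change is (1 − r²)/[2(1 − r)] = (1 + r)/2

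**Half-width of the 95% interval** for GGT minus IT = 1.96 × √(2 × 25 × variance/100).

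| r | k | Change | Adjusted | Ratio | Half-width, change → adjusted (points) |
|---|---|---|---|---|---|
| 0.5 | 1.0 | 1.00 | 0.75 | 0.75 | 1.39 → 1.20 |
| 0.6 | 1.0 | 0.80 | 0.64 | 0.80 | 1.24 → 1.11 |
| 0.7 | 1.0 | 0.60 | 0.51 | 0.85 | 1.07 → 0.99 |
| 0.5 | 0.8 | 0.84 | 0.75 | 0.89 | 1.27 → 1.20 |
| 0.6 | 0.8 | 0.68 | 0.64 | 0.94 | 1.14 → 1.11 |
| 0.7 | 0.8 | 0.52 | 0.51 | 0.98 | 1.00 → 0.99 |
| 0.6 | 1.2 | 1.00 | 0.64 | 0.64 | 1.39 → 1.11 |

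In participants, r = 0.5 with equal SDs means that about 150 with adjustment match 200 without (200 × 0.75). At r = 0.6 and k = 0.8 the matching number is about 189 (200 × 0.64/0.68 = 188.2).

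**Alternative model.** A longitudinal model that keeps baseline as an outcome but gives both arms one baseline mean was checked with equal SDs and equal correlations. Its week-12 standard error equals the adjusted one: 0.135, 0.122 and 0.101 SD at r = 0.3, 0.5 and 0.7. The change contrast gives 0.167, 0.141 and 0.110.

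**Validity.** In simulations with no arm difference (2,000 runs per setting, same r values), the rejection rate was 4.2% to 5.6% across the planned interaction test and the adjusted tests.

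**Power, as illustration only.** Take r = 0.5, equal SDs and a true week-12 difference of 0.4 SD. A single week-12 change contrast has 80.7% power and the adjusted contrast 90.4%. If the difference builds up linearly, the planned three-degree-of-freedom test has a simulated 69.8%. Of the 20.6-point gap (90.4 − 69.8), about 9.7 points (90.4 − 80.7) come from adjustment. The other 10.9 or so (80.7 − 69.8) come from testing three degrees of freedom rather than one named contrast.

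**The case against.** The case on the other side has real content.

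- **Baseline is not ignored.** The interaction already compares changes, and baseline as an outcome level is not itself a fault: the common-baseline-mean model keeps it there and loses nothing. The loss comes from letting the baseline mean differ by arm. This stands.
- **Not every term in the ANOVA is a change contrast.** The condition main effect averages over all four visits, so the point concerns the interaction only. This stands.
- **The gain may be small.** The ratio (1 + r)/2 needs equal SDs at baseline and week 12. Entry at 5 or more on either scale may narrow baseline spread, and the table shows ratios of 0.94 and 0.98 when it does. A reader might infer from the equal-SD rows that adjustment is worth 18% to 33% more participants (1/0.85 and 1/0.75). The documents give no SD or correlation to support that range. The gain could also be larger, if spread shrinks under treatment (the k = 1.2 row).
- **The half-widths are optimistic.** They use the maximum sample, an assumed 1:1 split and no dropout, and they ignore any shared variation among students treated in the same group. This stands for the absolute figures.
- **Randomisation is never stated.** A reader might call the change free. That follows only under random assignment, and the protocol says only that participants are assigned. Otherwise the two analyses can estimate different quantities, and a common baseline mean is not justified.

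None of this reverses the direction. Under random assignment the change variance exceeds the adjusted variance by a squared term, so in large samples adjustment cannot cost precision.

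**Conclusion.** The point holds as one of efficiency. Given random allocation, the planned interaction is no more precise than a baseline-adjusted comparison and usually less so. At week 12 the illustrative variance saving is 15% to 25% for r of 0.7 to 0.5 with equal SDs. It is about 6% at r = 0.6 and 2% at r = 0.7 when the baseline SD is 0.8 of the week-12 SD. Every size here rests on assumed values of r, the SDs and the allocation.

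Two stronger readings are not supported. A reader might infer that the planned test is invalid; the simulated type I error stays near 5%. A reader might also infer that adjustment would let the trial conclude that GGT and IT are comparable. It would not: the SAP states no margin, and a narrower interval has nothing to be judged against until one is set. That gap is separate and larger.

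**What to change.** 1. State in the SAP whether assignment is random and, if so, the ratio.
2. If it is random, replace the primary model with one in which weeks 4, 8 and 12 are the outcomes. Include condition, week, condition-by-week, baseline score on the same scale, and baseline-by-week. A longitudinal model with a common baseline mean is an equivalent choice.
3. Name the adjusted GGT-minus-IT difference at week 12 as the reported comparison, with its 95% CI, separately for PHQ-9 and GAD-7.
4. If assignment is not random, do not make the switch on precision grounds. State which quantity is to be estimated and justify the analysis on that basis.

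The cost is a short SAP amendment, with no new visits, measures or participants. It does replace the primary model and fix a week-12 estimand, so it should be made before outcomes are compared by arm. The comparability margin has to be set separately.
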